## Power Analysis

Hypothesis 1a is largely descriptive in nature, but all other hypotheses involve inferential tests of a within-group (repeated measures) effect. To evaluate statistical power, we calculated necessary sample sizes for a paired t-test. Analyses considered both a medium (0.35) and large (0.55) Becker g pre-post standardized mean difference ( $[M_{post} - M_{pre}]/SD_{pre}$ ) under two pre-post correlation conditions. With a Type I and II error set at 0.05 and 0.20, we estimated necessary sample sizes of 79 and 34 for medium and large

effect detection with the pre-post correlation equal 0.40. If the pre-post correlation was somewhat higher, at 0.60, necessary sample sizes drop to 54 and 23. Results suggest the study is powered to detect a moderate to large effect provided the pre-post correlation is of moderate strength.

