#### **D. Research Design and Methods (What, When, How, Where)**

##### **Study Design**

We will use a 2-arm randomized, controlled cross over trial design to evaluate the effectiveness of the mHealth Intervention. We will recruit up to 50 participants from three home visiting programs (SafeCare at NorthCare, Latino Community Development Agency [LCDA], and Parent Child Center [PCCT]). All three of these programs utilize the SafeCare home visiting model, which includes modules on healthy parent-child interactions and promoting parenting skills in high-risk families. We plan to recruit existing and new families in these programs and randomly assign them to receive either 2 weeks of the mHealth intervention + EMA data collection followed by 2 weeks of only EMA data collection or to receive 2 weeks of only EMA data collection followed by 2 weeks of mHealth intervention + EMA data collection. All participants will receive both conditions in counterbalanced order.

Study participation involves consenting to administrative record release and immediate baseline questionnaires assessing demographics, the child's exposure to adversity, parental exposure to childhood adversity, parent's emotional expression, emotion reactivity, and emotion regulation and the child's emotion regulation and development, ecological momentary assessment (EMA) at fixed times twice a day (morning and evenings), and final assessments, which will be the same as the baseline assessments.

**EMA Only Condition** In the EMA only condition, families will continue to receive services utilizing the SafeCare home visiting model, including modules on healthy parent-child interaction and promoting parenting skills in high-risk families, but they will not receive parenting tips via the mHealth app during this period. We plan to administer brief surveys via the mHealth app twice a day at pre-determined times (morning and evening). These surveys will ask parents to provide information about where they are and

with whom, their emotional state, recent parent-child interactions, current stressors or challenges, and their child's emotional and behavioral functioning. Parents will receive these twice daily surveys every day for two weeks.

[figure not shown]

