### **App Feasibility and Effectiveness Data**

We will also collect data on parents' perceptions of app feasibility and effectiveness via survey and a focus group selected from a subset of the 50 participants (up to n =30). We will also track app use (e.g., assessment response rates, number of missing assessments, time spent on app, type of OnDemand content viewed) to provide insight into participant compliance and app interaction.

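### The power conclusion does not hold at the plan's own medium effect of 0.35: the required 79 or 54 participants both exceed the enrolment limit of 50

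*Combined protocol and SAP*

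**What the plan says.** The Power Analysis section treats every hypothesis except 1a as a test of a within-group effect and sizes them together: "we calculated necessary sample sizes for a paired t-test". The inputs are explicit. On effect size: "Analyses considered both a medium (0.35) and large (0.55) Becker g pre-post standardized mean difference". On error rates: "With a Type I and II error set at 0.05 and 0.20", that is, 80% power. At a pre-post correlation of 0.40, "we estimated necessary sample sizes of 79 and 34 for medium and large" effects respectively. Then: "If the pre-post correlation was somewhat higher, at 0.60, necessary sample sizes drop to 54 and 23". The section closes with "Results suggest the study is powered to detect a moderate to large effect provided the pre-post correlation is of moderate strength".

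The number available is given elsewhere. Study Design: "We will recruit up to 50 participants from three home visiting programs". App Feasibility and Effectiveness Data also treats 50 as the whole sample: "a focus group selected from a subset of the 50 participants (up to n =30"). The Power Analysis section never sets its required sizes against 50 and states no allowance for loss, although the Withdrawal criteria section foresees withdrawals.

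**The concern.** The plan names two effects, medium (0.35) and large (0.55), and gives no separate value for moderate. The natural reading of the closing sentence is therefore that the study has 80% power from 0.35 upwards. Its own required sizes for 0.35 are 79 and 54, against at most 50 participants.

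The condition placed on the correlation does not repair this, because even the more favourable of the two correlations examined calls for more people than can be enrolled.

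At stake is how the results will be read. The section on potential benefits says the data will serve as pilot data for federal grant applications. If the study is believed to have 80% power at 0.35, a non-significant result will look like stronger evidence against a medium effect than it is.

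**Working it through.** **Inputs from the documents.** Paired t-test; Type I error 0.05; power 0.80; standardized change g = 0.35 or 0.55 (change divided by the pre SD); pre-post correlation r = 0.40 or 0.60 (all from Power Analysis); at most 50 participants (Study Design).

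**Assumptions.** The plan does not state sidedness; two-sided is inferred below. Pre and post SDs are taken as equal. Every participant supplies a complete pair unless stated otherwise.

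**Method.** With equal SDs, the SD of the difference is SD_pre × √(2(1 − r)), so the paired-test effect size is dz = g / √(2(1 − r)). Power comes from the noncentral t distribution with n − 1 degrees of freedom and noncentrality dz × √n.

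**Step 1: reproduce the plan's figures.**

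| g | r | dz | Plan's N | N, two-sided | N, one-sided |
|---|---|---|---|---|---|
| 0.35 | 0.40 | 0.35/√1.2 = 0.3195 | 79 | 79 | 62 |
| 0.55 | 0.40 | 0.55/√1.2 = 0.5021 | 34 | 34 | 26 |
| 0.35 | 0.60 | 0.35/√0.8 = 0.3913 | 54 | 54 | 42 |
| 0.55 | 0.60 | 0.55/√0.8 = 0.6149 | 23 | 23 | 18 |

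All four match the two-sided test exactly and none matches the one-sided test. The method and inputs are therefore those the plan used, and its sample-size arithmetic is right.

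**Step 2: compare with the limit of 50.** For g = 0.35 the shortfall is 79 − 50 = 29 at r = 0.40 and 54 − 50 = 4 at r = 0.60. For g = 0.55, both 34 and 23 fit.

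**Step 3: power with 50 complete pairs.** For g = 0.35 the noncentrality is 0.3195 × √50 = 2.26 at r = 0.40 and 0.3913 × √50 = 2.77 at r = 0.60.

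| g | r = 0.40 | r = 0.50 | r = 0.60 |
|---|---|---|---|
| 0.35 | 60.1% | 67.9% | 77.4% |
| 0.55 | 93.6% | 96.8% | 98.9% |

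**Step 4: what 50 pairs can detect.** Eighty per cent power at n = 50 needs dz of about 0.404. Then g = 0.404 × √(2(1 − r)):

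- r = 0.40: 0.404 × √1.2 = 0.44
- r = 0.50: 0.404 × √1.0 = 0.40
- r = 0.60: 0.404 × √0.8 = 0.36

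**Step 5: correlation needed for 0.35.** Setting 0.404 × √(2(1 − r)) = 0.35 gives r of about 0.625. The required N is 51 at r = 0.62 and 50 at r = 0.63.

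**Step 6: sensitivity to loss.** The documents give no loss rate, so these rates are assumed for illustration.

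| Loss | Pairs | Power for 0.35, r = 0.40 | Power for 0.35, r = 0.60 |
|---|---|---|---|
| 0% | 50 | 60% | 77% |
| 10% | 45 | 55% | 73% |
| 20% | 40 | 50% | 68% |

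The large effect is robust: power stays at 80% or more down to 34 analysed pairs at r = 0.40 and 23 at r = 0.60.

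**The case against.** **Moderate may mean something between the two benchmarks.** The closing sentence changes word, from medium to moderate. If it means an effect between 0.35 and 0.55, it is defensible with 50 complete pairs, since the detectable effects of 0.36 to 0.44 lie in that interval. But the plan gives no such value, and its only label below large is attached to 0.35. If an intermediate effect was meant, the number has to be stated.

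**The sentence is hedged and its inputs are visible.** It is conditional on the correlation, and 79 and 54 stand just before it. However, the comparison with 50 is not made in that section, and the condition fails at both correlations examined.

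**The gap at r = 0.60 is small.** This stands: four participants, or 2.6 percentage points of power. Only the r = 0.40 case is material on its own, although 50 is a ceiling and any loss widens both gaps.

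**The paired t-test is not the planned analysis.** This stands in part. It fits Hypotheses 1c and 2b closely, as they compare one baseline with one follow-up score. Hypotheses 1b and 2a use repeated EMA reports in a mixed model, and averages of many reports usually correlate more strongly than single scores. As an illustration, assume one report a day for 14 days per period, only a random intercept, and a daily intraclass correlation ρ of 0.1, 0.2 or 0.3. The two period means then correlate at 14ρ/(1 + 13ρ) = 0.61, 0.78 or 0.86. At 0.78 or more, power for 0.35 in period-mean SD units exceeds 90% with 50 pairs. Autocorrelation or responses that vary between parents would lower it. The shortfall is thus not established for 1b and 2a, but neither is adequate power: the plan gives no separate calculation and applies the paired t-test to them as well.

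**Conclusion.** The concern holds. At the only effect the plan labels medium, the required sizes exceed maximum enrolment at both correlations considered, and power with 50 complete pairs is 60% or 77% rather than 80%. The chance of missing a true change of 0.35 is thus about 40% or 23%, against the planned 20%.

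The fault is confined to the concluding sentence. The statement is right for the large effect. The result rests on the plan's own test and inputs, on two-sided testing (inferred because only that reproduces the stated sizes), on equal pre and post SDs, and on no loss. It applies most directly to Hypotheses 1c and 2b. It should be corrected, but it does not call the design or the analysis into question.

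**What to change.** Replace the closing sentence of Power Analysis with text such as:

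> With all 50 participants analysed, a two-sided 0.05 paired t-test has 80% power for standardized changes of about 0.44 (r = 0.40) or 0.36 (r = 0.60). Power for the medium effect of 0.35 is 60% (r = 0.40) or 77% (r = 0.60) and reaches 80% only if r is about 0.625 or higher; the large effect of 0.55 has at least 80% power at both correlations. These figures assume complete pairs and will be lower with loss to follow-up. The paired t-test is an approximation for the EMA mixed-model Hypotheses 1b and 2a, for which power was not calculated separately.

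If the investigators have an expected completion rate, the same figures can be given at that number of pairs.

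The cost is one sentence replaced by a short paragraph. Enrolment, design and analysis do not change; the only drawback is a less favourable stated power at 0.35.

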#### **J. Data and Safety Monitoring Plan**

Participant safety will be monitored in the following ways. First, the service agency will routinely complete Critical Incident Reports (CIR's) on all cases experiencing any sort of adverse event, regardless of whether the event might be related to study participation. This includes incidents such as any hospitalization, any child welfare reports, any serious medical condition, etc. This also includes incidents that are not adverse events such as unplanned dropout from service. The research team has established a procedure to receive these CIR's electronically on all study subjects, and each report will be reviewed by the PI, and passed on to the IRB as prescribed in our IRB regulations. Second, data collectors are trained to recognize and report any potential adverse events they might observe or that are reported to them by participants. Other organizations, such as the OUHSC Institutional Review Board may inspect and/or copy research records for quality assurance and data analysis.

#### **K. Confidentiality**

All consent forms will be collected and retained automatically on the OUHSC server in a group user protected folder. If paper copies are collected, they will be scanned to the server and stored in a folder in a locked cabinet behind a locked door in CCAN (which also requires a security badge for entry).

Data will be stored with identifiers for up to 10 years past the study conclusion date. Data will be stored in REDCap and on SQL Server. Some data may be manipulated and stored on the CCAN group rights protected folder on the server. SQL Server and REDCap have user rights protected groups, and to access SQL Server, the user must be connected to Pulse Secure VPN.

